**REVISION HISTORY**

*This Revision History table is provided for the benefit of study team version control. If this table will not be useful please delete it.*

Revision #	Version Date	Summary of Changes	Consent Change?
1	4.24.23	Addition of Twilio to send secure text messages through REDCap	yes
2	6.9.23	Addition of exploratory aim of genetic variation and collection of voluntary salivary samples from all participants	yes
3	6.21.23	Clarification of reconsenting process for participants who turn 18 years old during study	
4	7.12.23	Clarification of eligibility criteria, must be an ENDS user (cannot be solely a traditional cigarette user, can be co-user)	
5	7.28.23	Addition of hospital staff as participants and information about the interviews for them	
6	7.28.23	Inclusion of vulnerable population, wards of the state	
7	2.21.24	Addition of another salivary testing option for participants.	yes
8	5.24.24	Addition of option for blood salvage samples for genomic sequencing.	yes
9	8.30.24	Adding additional study site, Children's Hospital of Los Angeles (CHLA). The current	Yes

		study PI ([name]) will be starting a position there on November 1, 2024. At the time of her departure we will change the CMH study PI to [name] (currently a Co-Investigator). CHLA will be added as a study site but will complete external reliance on the CMH IRB and no data collection will occur at CHLA.	
--	--	---	--

## STUDY INFORMATION

### 1.0 Study Summary\*

#### 1.1 Synopsis

Study Title	Development and Implementation of a Tobacco and ENDS Use Intervention for Adolescents and Young Adults in the Pediatric Hospital
Study Design	Randomized controlled pilot study with 3-month follow up to evaluate preliminary efficacy as well as implementation outcomes (i.e., acceptability, feasibility, fidelity) of a tobacco use and vaping cessation program. All data collection will occur at Children's Mercy Hospital (CMH) but we will have a second study site (CHLA; added due to change in position of PI [name]) where no data collection will occur, but data containing PHI may be shared.
Primary Objective	We will evaluate preliminary efficacy (i.e., 30-day self-reported abstinence with biochemical verification) as the primary outcome.
Secondary Objective(s)	We will assess self-reported motivation and confidence to quit and implementation outcomes (i.e. acceptability, feasibility, and fidelity) immediately post-intervention and at 3-month follow up.
Study Population	Adolescents and young adults (AYAs; 14-21 years old) admitted to the hospital
Sample Size	144 AYA, up to 144 parents, up to 10 hospital staff
Study Duration for Individual Participants	3 months
Study Specific Abbreviations/ Definitions	Adolescents and young adults (AYAs) electronic nicotine delivery system (ENDS) American Academy of Pediatrics (AAP) United States (US) United States Preventive Service Task Force (USPSTF) Motivational interviewing (MI) SBIRT (Screening, Brief Intervention, Referral to Treatment) clinical decision support (CDS) Emergency department (ED) Nicotine replacement therapy (NRT) Electronic health record (EHR) Consolidated Framework for Implementation Research (CFIR) Randomized controlled trial (RCT)

### 2.0 Objectives\*

#### 2.1 Purpose, specific aims or objectives:

**Design and iteratively refine a tobacco and ENDS use intervention for AYAs.** We will draw on promising primary care and hospital-based approaches to develop and iteratively refine, based on survey and interviews of key stakeholders, a novel intervention to screen for and treat current tobacco and ENDS use in hospitalized AYAs.

**Evaluate preliminary efficacy and implementation outcomes of the tobacco and ENDS use intervention.** We will conduct a randomized pilot trial with 3-month follow up to assess preliminary efficacy and implementation of the intervention in hospitalized AYAs with current tobacco and ENDS use. Self-reported 30-day abstinence with biochemical verification at 3 months will be the primary outcome and secondary outcomes will include implementation measures (e.g., acceptability, feasibility, fidelity).

**Exploratory secondary aim:** We will explore the impact of individual-level factors (e.g., CYP2A6 genotype, nicotine metabolite ratio, sex) at baseline with our primary outcome (past 30 day ENDS use abstinence).

## **2.2 Hypothesis to be tested/Exploratory study design:**

We hypothesize the intervention arm will have higher rates of biochemically confirmed self-reported tobacco use abstinence (preliminary efficacy; primary outcome) compared to the control arm at 3 month follow up.

## **3.0 Background\***

Tobacco use is the single leading cause of preventable death, disability and disease in the United States (US). Adolescence is a critical developmental period for intervention because 90% of adult tobacco users initiate during this period. Although tobacco control efforts have led to declining rates of combustible cigarette use, electronic nicotine delivery system (ENDS) use among youth has risen dramatically in the past decade. ENDS, which include electronic or “e”-cigarettes, pod-based or disposable vaping devices, and vape pens, are now the most common tobacco product used by adolescents and young adults (AYAs). Between 2011-20, current (past 30-day) ENDS use increased from 1.5% to 20% among high school students and from 0.6% to 5% among middle school students. ENDS use is linked with increased use of cigarettes, alcohol and other illicit substances, as well as adverse health outcomes among AYAs. Recently there was an outbreak of hospitalizations for e-cigarette and vaping-associated lung injury including among youth (≤ 18 years).

The American Academy of Pediatrics (AAP) and the US Preventive Service Task Force (USPSTF) recommend counseling using the 5 A’s Framework (Ask, Advise, Assess, Assist, Arrange) and motivational interviewing (MI) techniques to address tobacco use at every adolescent clinical visit. This recommendation is based largely on research from the primary care setting, although many adolescents do not routinely attend primary care visits. With more than 1.5 million AYA hospitalizations annually, the hospital setting offers an untapped venue for identifying and treating AYA cigarette and ENDS use. Many hospitalized AYAs are at increased risk for tobacco use as well as tobacco-related poor health outcomes due to underlying comorbidities (e.g., mental health disorders, diabetes, asthma). In addition, the rising prevalence of ENDS use may be linked with increased risk for hospitalizations for respiratory illnesses as well as an increased risk for unrecognized and untreated nicotine withdrawal among hospitalized AYAs. Although research on tobacco and ENDS use among hospitalized AYAs is sparse, our preliminary data indicate that 28% report any tobacco use, and 15% report current ENDS use.

While there is strong evidence supporting the feasibility and effectiveness of treating tobacco use during adult hospitalizations and promising evidence for substance use treatment (e.g., alcohol) during

hospitalization among AYAs, no interventions for tobacco and ENDS use have been developed or tested in the pediatric hospital setting. In primary care-based tobacco treatment for AYAs there are limited ENDS use treatment interventions. In this proposal, we aim to address these limitations by initiating a line of research focused on treating tobacco and ENDS use among AYAs in the hospital.

Drawing on related work in the hospital and primary care settings, we will adapt components of the most efficacious tobacco and ENDS use interventions (e.g., 5 A's Framework, MI) to design an intervention that accounts for important hospital-specific contextual factors. We will use the Proctor and CFIR (Consolidated Framework for Implementation Research) frameworks to evaluate implementation such as determining the optimal process for tobacco and ENDS use screening and treatment while managing acute illness; coordinating care with the medical team; and using confidential computerized decision support (CDS) systems to achieve systematic and high-quality implementation. We will also identify and utilize feasible post-discharge follow-up strategies.

## **4.0 Study Design\***

### Health Services/Programmatic Activities

Design and iteratively refine a tobacco and ENDS use intervention based in clinical practice guidelines for AYAs

### Research Activities

- Conduct a pilot RCT to assess implementation of the evidence-based intervention in the pediatric hospital setting with 3-month follow up to assess preliminary efficacy and implementation outcomes. We will evaluate preliminary efficacy (i.e., 30-day self-reported abstinence with biochemical verification) as the primary outcome. We will also assess self-reported motivation and confidence to quit and implementation outcomes (i.e. acceptability, feasibility, and fidelity) immediately post-intervention and at 3-month follow up. We will conduct 4 follow up phone sessions with AYA post hospitalization. These phone calls will consist of counseling provided by the health educator and will last approximately 30 minutes. Parents of AYA will complete a post intervention survey. Hospital staff will be asked to complete a post intervention survey and interview.

All data collection will occur at Children's Mercy Hospital (CMH) however we will have a second study site (CHLA; added due to change in position of PI [name] November 1, 2024) where no data collection will occur, but data containing PHI may be shared for analysis.

## **5.0 Research Interventions\***

**5.1 Description:** We will conduct a prospective, pilot trial with 3-month follow up to assess preliminary efficacy and implementation outcomes. Hospitalized AYAs with current (past 30-day) ENDS use (including those with co-use of cigarettes) will be randomized 2:1 to receive either novel intervention or control intervention that will consist of brief advice and printed quit line referral as part of their clinical care. We will evaluate preliminary efficacy (i.e., 30-day

## SHORT TITLE: Tobacco Inpatient Intervention

self-reported abstinence with biochemical verification) as the primary outcome. We will also assess self-reported motivation and confidence to quit and implementation outcomes (i.e. acceptability, feasibility, and fidelity) immediately post-intervention and at 3-month follow up.

We will screen the EMR to identify potential eligible participants and send a text page to the medical team to notify them that we will approach the potential participant. The text page will state "Your patient is potentially eligible to participate in [name] research study about vaping and tobacco use. Please call us if you have concerns about our team approaching the patient." The study team will then approach the eligible participant and give brief information about the study (e.g., "We are doing a research project to learn how we can help adolescents and young adults stop vaping and using tobacco products. Are you interested in hearing more about this?"). The study team will then review and consent the eligible participants. Randomization of consented participants will be stratified on sex and age using a 2:1 ratio within strata via computer generated assignment sequence placed in sequentially numbered sealed envelopes. Control participants will receive brief advice from the health educator regarding tobacco and ENDS use cessation and printed referral to a quit line. Intervention participants will receive our vaping and tobacco use cessation intervention based in clinical practice guidelines and administered by a health educator. Intervention participants will be eligible to receive a prescription for nicotine replacement therapy based on current clinical practice guidelines if they demonstrate risk for nicotine withdrawal. All participants will complete a post-intervention survey and a 3-month survey sent via email, text message via Twilio, and/or mailed paper survey so the research team is not directly involved in outcome data collection. Four phone calls will be conducted on the intervention group post hospitalization to provide smoking cessation counseling. These calls will take approximately 30 minutes. Parents/guardians of AYAs will be asked to complete a post-intervention survey which will be administered by the health educator and will take approximately 15 minutes.

Hospital Staff will be asked to complete a post-intervention survey and interview conducted by the health educator to assess acceptability and disruption of the intervention, it will take approximately 10 minutes, the only PHI that will be collected is to compensate them and will include no sensitive data.

Participant demographics and clinical characteristics (e.g., age of initiation, nicotine dependence) will be assessed at baseline. Preliminary efficacy will be assessed via self-reported 30-day point prevalence tobacco/ENDS abstinence using the timeline follow-back method at 3-month follow-up. To obtain a biochemically verified outcome and to encourage accurate self-reporting we will assess salivary cotinine via mailed samples from all participants (not currently on NRT) who report abstinence. We will assess this by either mailing a saliva specimen home collection kit to then be return mailed (pre

addressed and paid) to our study team or we will also offer the option of completing a home saliva cotinine test which do not require return mailing. For this option home saliva cotinine tests will be mailed to the participant. The study team will then schedule a secure Microsoft Teams video call to witness saliva test completion and results or photos of the test results can be emailed at a convenient time to [[contact]](mailto:[contact]) . Although accurate verification will not be possible with participants who are occasional users or those on NRT, this will also allow us to evaluate the feasibility of confirming abstinence by collecting saliva specimens by mail or completing witnessed (via Microsoft Teams secure video or securely emailed photos) home saliva cotinine tests in this population which will be informative for future studies with daily ENDS users. Secondary efficacy outcomes will include self-reported motivation and confidence to quit immediately post-intervention and at 3-month follow up. We will assess acceptability with the overall intervention and intervention components via survey immediately post intervention (AYAs and parents) and at 3 month follow-up (AYAs). We will also explore our secondary objective by obtaining a voluntary saliva or salvage leftover blood samples at baseline from all participants to assess genotyping the impact of individual-level factors (e.g., CYP2A6 genotype, nicotine metabolite ratio, sex) at baseline with our primary outcome (past 30 day ENDS use abstinence).

Acceptability will also be evaluated via participant enrollment and session completion rates. Study Procedures: Data from AYAs and parents/guardians will be collected using confidential electronic survey collection via REDCap.. AYAs who decline to participate will be asked to provide age, sex, race and ethnicity to facilitate identification of participation bias.

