Measures: *Participant demographics and clinical characteristics* (e.g., age of initiation, nicotine dependence) will be assessed at baseline. The outcome measures, method of assessment, relevant stakeholders and detailed description are depicted in Table 3 and sample survey items in Table 4. *Preliminary efficacy* will be assessed via self-reported 30-day point prevalence tobacco/ENDS abstinence using the timeline follow-back method at 3-month follow-up. To obtain a biochemically verified outcome and to encourage accurate self-reporting we will assess salivary cotinine from all participants (not currently on NRT) who report abstinence. We will assess this by either mailing a saliva specimen home collection kit to then be return mailed (pre addressed and paid) to our study team or we will also offer the option of completing a home saliva cotinine test which do not require return mailing. For this option home saliva cotinine tests will be mailed to the participant. The study team will then schedule a secure Microsoft Teams video call to witness saliva test completion and results or photos of the test results can be emailed at a convenient time to [contact]. If video call is performed the Microsoft Teams video call will not be recorded. If photos are emailed, the photos will be uploaded to REDCap and then deleted from the email. Secondary efficacy outcomes will include self-reported motivation and confidence to quit immediately post-intervention and at 3-month follow up. We will assess *acceptability* with the overall intervention and intervention components via survey immediately post intervention (AYAs and parents) and at 3 month follow-up (AYAs). Acceptability will also be evaluated via participant enrollment and session completion rates. *Feasibility* will be assessed via intervention duration in minutes from audio recordings and [name] and the health educator will complete a brief survey and record field notes to assess feasibility (e.g., impact on workflow, disruption, suitability). To assess *fidelity* we will review audio recordings and rate health educator intervention and control sessions based on a previously developed fidelity rating scales.

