## 10.0 Additional Research Activities

## SHORT TITLE:

**10.1** Data collection from the medical record: The research team will use a REDCap instrument to collect some demographic information (eg, age, insurance type) from the medical record for each participant.

Additionally, upon completion of enrollment, we will collect additional medical record data based on Cerner orders and/or prescription information (to assess for prescription of NRT).

**10.2** Refusal Log: The study team will maintain a refusal log to assess potential differences between AYAs that participate and those that do not. AYAs who decline to participate will be asked if they will provide information anonymously. If they agree to do this, they will complete an anonymous survey to assess age, sex, gender, race/ethnicity, primary language, and reason for not participating. This survey will be administered via REDCap/tablet computer. If the adolescent declines to complete the refusal survey, the study team member will complete survey items on age and sex (available via EHR) and reason for study declination, if provided.

**10.3** Blood and Other Specimen Collection:

- To explore the impact of genetic variation on electronic cigarette use, nicotine dependence and cessation outcomes, DNA will be isolated from each participant and genotyping/sequencing will be completed by CMRI Genomics core or a similar service. This will allow for detection of known SNPs of interest and creation of an exploratory dataset for future inquiry as new questions arise. To evaluate this exploratory outcome we will collect a salivary or salvage leftover blood (collected during hospital stay) samples from all participants at baseline.
- A saliva sample kit will be mailed to the participant's home with a pre-paid label for their return of the sample or participants will have the option of completing a salivary cotinine test at home that will be witnessed by a study team member through secured Microsoft Teams video calling or photos will be securely emailed to a research specific email address. If using the return mailing option participants will collect saliva according to included instructions and send the sample back in the package we provide them.
- No extra samples will be collected during this time.

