## 17.0 Payment, Reimbursement and Tangible Property provided to subjects\*

Is payment, reimbursement, or tangible property part of the study?

Yes       No *(If No, delete the following subsections)*

**17.1 Payment to Subjects:** If providing payment for participation (e.g. cash equivalent for participation, payment for time off work), select the form of payment:

- Greenphire/ClinCard
- Gift Card: (Merchant: \_\_\_\_\_)
- Other: \_\_Clinical Conductor (CCpay)\_\_\_\_\_

*Note: "Gift Card" and "Other" options require approval by Research Administration. Upon submission in myIRB, ORI staff will initiate the Research Administration approval process.*

SHORT TITLE:

Payment Schedule:

Formative stage: Parents of AYA will receive \$20 for participation.  
Hospital staff of AYAs will receive \$10 for participation.

Research stage: Pilot RCT: AYAs will receive \$15 for study enrollment and \$20 for 3-month follow up survey completion. For eligible participants who agree to complete a saliva sample at the 3 month follow up they will receive \$25 once the sample is completed/received. Total potential payment for one AYA participant is \$60. We will also provide NRT prescription free of charge for AYA participants assigned to the intervention group and for which this is clinically indicated.

**17.2 Reimbursement:** N/A

**17.3 Tangible Property:** N/A

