## SHORT TITLE:

to our study team or we will also offer the option of completing a home saliva cotinine test which do not require return mailing. For this option home saliva cotinine tests will be mailed to the participant. The study team will then schedule a secure Microsoft Teams video call to witness saliva test completion and results or photos of the test results can be emailed at a convenient time to [[contact]](mailto:[contact]), a secure email address created specifically for this research study. Although accurate verification will not be possible with participants who are occasional users or those on NRT, this will also allow us to evaluate the feasibility of collecting saliva by mail or completing secure video or photos witnessed home saliva cotinine tests in this population which will be informative for future studies with daily ENDS users. Secondary efficacy outcomes will include self-reported motivation and confidence to quit immediately post-intervention and at 3-month follow up. We will assess *acceptability* with the overall intervention and intervention components via survey immediately post intervention (AYAs and parents) and at 3 month follow-up (AYAs). Acceptability will also be evaluated via participant enrollment and session completion rates. *Feasibility* will be assessed via intervention duration in minutes from audio recordings and [name] and the health educator will complete a brief survey and record field notes to assess feasibility (e.g., impact on workflow, disruption, suitability). To assess *fidelity* we will review audio recordings and rate health educator intervention and control sessions based on a previously developed fidelity rating scales To assess *preliminary efficacy*, differences in self-reported and biochemically verified 30-day tobacco/ENDS use abstinence at 3-month follow up (primary outcome) will be analyzed using a generalized linear model assuming an underlying binomial distribution and logit link function to compare between study arms. Motivation and Confidence to quit will be analyzed using a repeated measures analysis of variance. Potential differential outcomes based on sex and demographic factors will be explored. Chi-square (categorical variables) and Wilcoxon Rank Sum (continuous variables) tests will be used to assess participation bias. For acceptability, we will calculate the proportion of AYA participants and parents/guardians in the intervention arm with mean ratings of satisfaction and acceptability of  4 on the 5-point Likert scale. In addition, frequencies and percentages will be used to describe the enrollment and session completion rate. For *feasibility* we will conduct thematic analysis of field notes and conduct simple descriptive analyses (means, frequencies, percentages) of the brief survey items completed by [name] and the health educator and session length data. *Fidelity* will be summarized utilizing similar descriptive analyses of the fidelity ratings (e.g., percentage of intervention steps completed; mean rating of key MI skill adherence).

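### Protocol sections 5.1 and 27.1 call an emailed photo of a home cotinine test 'witnessed', but nobody observes that test and no identifier or date is required in the image

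*Protocol*

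**What the plan says.** The primary outcome is self-reported and biochemically verified 30-day abstinence at 3 months (protocol section 27.1, Table 3). Salivary cotinine is tested only in participants who report abstinence and are not on NRT. The protocol offers three routes: a specimen mailed back, a home test done on a video call, and a home test reported by photo.

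For video, section 5.1 plans a "secure Microsoft Teams video call to witness saliva test completion and results". For the photo route it says that "photos of the test results can be emailed at a convenient time to" a study address. The same section then covers both with one label, "completing witnessed (via Microsoft Teams secure video or securely emailed photos) home saliva cotinine tests in this population", and section 27.1 has "completing secure video or photos witnessed home saliva cotinine tests in this population". Section 10.3 draws the line differently: the home test is "witnessed by a study team member through secured Microsoft Teams video calling or photos will be securely emailed to a research specific email address", so the team member's witnessing attaches to the video and the photo stands as an alternative.

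The only handling rule for photos is in section 9.0: "If photos are emailed, the photos will be uploaded to REDCap and then deleted from the email". The SAP (Assessments) describes mailed samples only and mentions neither the home test nor the photo.

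**The concern.** Testing is confined to people who say they have quit, so its job is to catch false reports. On the photo route, the person whose report is being checked decides what is photographed and when it is sent. Nothing in the plan would exclude a picture of someone else's negative strip, one strip photographed by two participants, or a strip from another date. Any of these would turn an unverified self-report into a verified one.

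The 'witnessed' label hides this in the two sections that describe the outcome and its analysis. Because the analysis does not separate results by route, a reader of the trial report could not tell how much of the verification was actually observed.

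**Working it through.** **1. The routes side by side**

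| Route | Collection observed? | Identifier or date required? | Called 'witnessed'? |
|---|---|---|---|
| Returned specimen | No | None stated for cotinine kits | No |
| Home test, video | Yes, completion and result | Seen live | Yes (5.1, 10.3, 27.1) |
| Home test, photo | No | None stated | Yes (5.1, 27.1) |

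**2. Search for a safeguard elsewhere**

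- Section 28.1 requires a record number on saliva or salvaged blood held in the repository freezer. It does not mention home strips or photos.
- Sections 23.1 and 28.0 link surveys by a code that the participant creates, and say the team cannot tie survey data to identity. How a photo is joined to the right self-report is therefore also unstated.
- Section 11.0 gives a 10-14 week window for the survey. No window is given for the test or the photo.
- Section 27.1 and the SAP (Measures and Statistical Analysis) fit one binomial model with a logit link, with no term or sensitivity analysis for route.

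**3. The plan's own figure**

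The sample size text gives a margin of error of 10% or less at a proportion of 50%. With ME = 1.96 × √(0.25/n):

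- n = 144: 8.2%
- n = 96: 10.0%
- n = 48: 14.1%

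The stated 10% reproduces for the whole sample and the intervention arm, but not for the control arm. It neither supports nor weakens this point: it measures sampling error, and false verification is a bias that it does not contain.

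**4. Effect of one false verification** (all randomised participants in the denominator)

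- Intervention: 1/96 = 1.04 points.
- Control: 1/48 = 2.08 points.

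**5. Illustration, on assumed rates**

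The documents give no abstinence rate, photo share or falsification rate. Assume true abstinence of 10% (control) and 25% (intervention), odds ratio 3.00. Let a share f of true non-abstainers be falsely verified, equally in both arms. Then observed p = p + (1 − p)f.

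| f | Control | Intervention | False verifications, control / intervention | Odds ratio |
|---|---|---|---|---|
| 2% | 0.10 + 0.90 × 0.02 = 0.118 | 0.25 + 0.75 × 0.02 = 0.265 | 0.9 / 1.4 | 2.69 |
| 5% | 0.145 | 0.2875 | 2.2 / 3.6 | 2.38 |
| 10% | 0.190 | 0.325 | 4.3 / 7.2 | 2.05 |

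The counts are 48 × 0.90 × f and 96 × 0.75 × f. Equal false verification pulls the odds ratio towards 1. Unequal false verification could push it either way. For example, with 10% true abstinence in both arms and f of 5% in the intervention arm only, the odds ratio is (0.145/0.855)/(0.10/0.90) = 1.53 with no true effect.

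**The case against.** The strongest reply is that the problem is narrow. Sections 9.0 and 10.3 already attach witnessing to the video, and the loose label sits in the feasibility sentences of 5.1 and 27.1, where it drives no analysis. That stands, and it limits the rewording to those two sections. It does not answer the lack of any identifier or date in the image.

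Nor is the photo wholly unanchored. Tests are mailed to the participant after a report of abstinence, photos go to a study-specific address, and participants' email addresses are recorded (25.4). This also stands, but it identifies a sender at most. No check against the address is planned, the photo is deleted from the email after upload, and a send date does not show when the test was done or whose saliva it was.

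A third reply is that this is a pilot, that it concedes imperfect verification, and that a low-burden option suits adolescents. The photo option is indeed defensible. But the concession covers occasional users and NRT users, not photos. The feasibility of confirming abstinence by these routes is also one of the study's own products, and the SAP says a fully powered trial will build on it.

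A reader might go further than the documents allow in three ways:

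- **That returned specimens are secure because they belong to a mailed kit.** No section states such a link for cotinine kits, and that collection is unobserved too.
- **That the $25 rewards faking.** Section 17.1 pays "once the sample is completed/received", with no negative result required.
- **That the error would favour the intervention.** Greater pressure to appear abstinent in that arm is conjecture.

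**Conclusion.** The point holds as a worthwhile, low-cost improvement to the verification of the primary outcome. Sections 5.1 and 27.1 credit the photo route with observation that it does not have, and the plan sets no condition that would exclude a borrowed, shared or old strip. Lack of observation is common to both non-video routes; the label and the ease of sharing or reusing an image are specific to photos.

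The firm part of the size is the shift per false result, 1.0 or 2.1 points, assuming all 96 and 48 participants are in the denominators. The odds ratios in the working are illustrations on assumed rates. The documents support neither a number of false verifications nor a direction of bias, so this is not evidence that the primary comparison is invalid. The conclusion rests on the protocol and SAP alone; the separate IRB documents that the protocol refers to were not available.

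**What to change.** 1. In sections 5.1 and 27.1, use 'witnessed' for the video call only. Sections 9.0 and 10.3 can stay.
2. Mark each mailed home test with a study code that can be joined to the participant's survey record, and reconcile this with the participant-created code in sections 23.1 and 28.0. Without that link the mark does not connect the photo to the self-report.
3. Accept a photo only if the marked test, its result and a handwritten date are all visible. No face is needed, in keeping with section 25.4, which does not list face images as recorded.
4. Record the verification route (returned specimen, video, photo) in REDCap and report the counts by arm.
5. Bring the SAP into line with the three routes.
6. Add one sensitivity analysis to the SAP: the same binomial model with photo-only results counted as not verified. It will also reclassify genuine abstainers who chose photos, so it should be read beside the route counts by arm.

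The cost is a wording amendment, marking the kits, one REDCap field and one extra model run. A few photos will be rejected and have to be repeated. Marking stops shared and reused strips but cannot show whose saliva was tested, so steps 3 and 6 are both needed. Any photos already received without a mark should be coded as photo-only.
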